14.1.1.1 Development of the Performance Goal

The PG was derived from literature for the Perclose ProGlide® (Abbott Vascular, Inc., Redwood City, CA, USA), a suture-mediated device indicated for the closure of large arterial access sites.

14.1.2 Primary Safety Endpoint

The primary safety hypothesis will be tested by comparing the primary safety endpoint, freedom from major complications of the target limb access site within 30 days post-procedure, against a performance goal.

The comparison to the performance goal will be based on the following statistical hypothesis test:

$$H_0: p \leq 85.2\%$$

$$H_A: p > 85.2\%$$

where p is the safety endpoint rate for the test device.

Assuming similar performance as ProGlide (an event-free rate of 94%), one-sided alpha = 0.05, the sample sizes for various levels of power are:

Table 4: Primary Safety Endpoint Sample Sizes for Various levels of Power

Power	Sample Size	Minimum # of Event Free Patients needed to reject the H_0
81.3%	78	72
85.6%	86	79
88.3%	95	87

14.1.2.1 Development of the Performance Goal

The observed rate of major complications for ProGlide was 6% (3/50), with a one-sided exact binomial upper 95% confidence bound of 14.8%. In terms of an event-free rate, these quantities are mathematically equivalent to an observed event-free rate of 94%

with a lower confidence bound of 85.2%. Accordingly, for the current study, a value of 85.2% is proposed for a performance goal for the primary safety endpoint based on the event-free rate.

14.2 Statistical Analyses

14.2.1 General Considerations

Except where otherwise specified, the following general principles apply to the planned statistical analyses. All statistical analyses will be conducted using {SAS version 9.3 or later (SAS Institute Inc., Cary, NC)} or other widely accepted statistical or graphical software as required.

14.2.1.1 Descriptive Statistics

Continuous data will be summarized with mean, standard deviation, median, minimum, maximum, and number of evaluable observations. Categorical variables will be summarized with frequency counts and percentages. Confidence intervals may be presented, where appropriate, using the t-distribution for continuous data and exact binomial method for categorical variables.

14.2.1.2 Study Visit

Study visit Day 0 is the date of the index procedure. Day in the study will be calculated relative to the index procedure as follows:

Study Day = Assessment Date – Index Procedure Date

Each subject duration in the study will be based on the last study contact date, which is the latest date of all follow-up visits, assessments, adverse event onset or resolution, and study exit, including date of death.

Duration will be calculated as follows: Duration Days = Start Date – End Date

14.2.1.3 Visit Windows

Unless otherwise specified, visit assessments will be analyzed for each analysis time point according to the visit entered in the electronic Case Report Form (eCRF).

14.2.1.4 Statistical Significance

Unless otherwise specified, hypothesis testing will be performed at the two-sided 0.05 significance level. P-values will be rounded to three decimal places. If a p-value is less

than 0.001 will be reported as "<0.001". If a p-value is greater than 0.999, it will be reported as ">0.999".

14.2.1.5 Reporting Precision

Unless otherwise specified, the following conventions will apply for data display. In general, percentages will be displayed to 1 decimal place. Percentages <0.05% will be reported to 2 decimal places. For continuous parameters, means and medians will be reported to 1 additional decimal place than the measured value. In contrast, the standard deviation will be reported to 2 additional decimal places than the measured value. Minimum and maximum values will be reported to the same precision as the measured value.

14.2.2 Analysis Populations

14.2.2.1 Full Analysis Set

The full analysis set (FAS) as defined by the ICH E9^v as "The set of subjects that is as close as possible to the ideal implied by the intention-to-treat principle." The guideline also defined the Intention-To-Treat Principle as the effect of a treatment policy can be best assessed by evaluating based on the intention to treat a subject (i.e., the planned treatment regimen) rather than the actual treatment given. Therefore, the FAS includes all patients that were consented, enrolled, and met the inclusion/exclusion criteria.

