14.2.2.2 Per-Protocol Analysis Set

The protocol definition of the TTH endpoint includes only those patients that received the test device and did not have adjunctive therapy other than light compression applied to the access site manually, with a dressing, or as per the investigator's standard procedure for suture-mediated closure devices. Therefore, the per-protocol analysis set (PPS) includes those patients in the FAS where the patient received the test device and did not have adjunctive therapy other than light compression.

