14.2.2.3 Full Roll-In Analysis Set

The full roll-in analysis set (FAS_RI) are those patients that meet the same criteria as the FAS but are identified as roll-in patients.

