14.2.2.6 Safety Analysis Set

Due to the challenges during the pandemic, the number of patients in a non-missing primary safety endpoint may drop below the lowest accepted power (80%) for approval trial design (< 78 patients). If the number of patients in the FAS is ≤ 78 , the safety analysis set will include the patients in the FAS and the last 18 sequentially enrolled patients from the FAS_RI. If the number of patients in the FAS is > 78 , then the safety analysis set will only include FAS patients.

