14.2.10.2 Primary Safety Analysis

The primary safety endpoint will be evaluated using the FAS or the safety analysis set if roll-ins are needed. The endpoint will be presented as the proportion of subjects with

freedom from primary safety endpoint and the lower 95% confidence limit using the Clopper-Pearson exact method^{vi}. If the one-sided 95% confidence limit is greater than 85.2%, then the device will have met the performance goal for safety.

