14.2.10.2.1 Sensitivity Analyses

There will be three sensitivity analyses:

1. The primary safety endpoint analysis will be repeated with the FAS patients only if FAS_RI patients are added to the safety analysis set
2. Tipping analysis based on missing data in the safety analysis set, as described in section 14.2.6.
3. The primary efficacy endpoint analysis will be repeated with the FAS_RI and the safety analysis set combined.

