14.2.10.3 Secondary Endpoints

No formal hypothesis tests for the secondary and exploratory endpoints will be performed; endpoints will be summarized using the FAS with descriptive statistics.

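### Read literally, the FAS drops a patient treated with the device whose eligibility breach is found afterwards, and no other analysis set or safety sensitivity analysis brings that patient back

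*Protocol*

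**What the plan says.** The protocol and SAP define the analysis sets in the same words.

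- **FAS (protocol 14.2.2.1, SAP 7.2.1).** The paragraph sets out to define a set "as close as possible to the ideal implied by the intention-to-treat principle". It then concludes that "the FAS includes all patients that were consented, enrolled, and met the inclusion/exclusion criteria".
- **Enrolment (protocol 4, SAP 4).** A subject counts as enrolled only after consenting and meeting all eligibility criteria; the SAP adds the intra-procedural ones. The FAS sentence lists meeting the criteria as a further condition beside enrolment.
- **Roll-in set (protocol 14.2.2.3, SAP 7.2.3).** FAS_RI consists of "those patients that meet the same criteria as the FAS but are identified as roll-in patients".
- **PPS (protocol 14.2.2.2, SAP 7.2.2).** It "includes those patients in the FAS where the patient received the test device", so it lies inside the FAS.
- **Primary safety (protocol 14.2.10.2, SAP 7.7.2).** "The primary safety endpoint will be evaluated using the FAS or the safety analysis set if roll-ins are needed". If roll-ins are needed, "the safety analysis set will include the patients in the FAS and the last 18 sequentially enrolled patients" from FAS_RI (protocol 14.2.2.6, SAP 7.2.6).
- **Secondary endpoints, including all adverse events from device use (protocol 14.2.10.3, SAP 7.7.3).** These "endpoints will be summarized using the FAS with descriptive statistics".
- **Eligibility check (protocol 7.2).** The investigator checks the intra-procedure criteria before the device is used. A subject who fails is a screening failure and does not receive the device.
- **Disposition (protocol 14.2.8, SAP 7.5).** Consented subjects who do not meet all criteria, glossed as screening failures, are left out of the analyses and appear only in an accountability table.
- **Exclusion 7 (protocol 4.1).** It covers a class of drug received before, during or after the procedure.

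**The concern.** The safety question is whether patients stay free of major complications after the device is used. Who counts in the denominator should therefore not depend on information that arrives after device use. In a single-arm trial the outcome may already be known when source verification turns up a breach, so a rule that then removes the patient could remove failures selectively. Such a rule also does not sit with an intention-to-treat aim.

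The primary result rests on very few events: the plan's own table allows 6 failures in 78 patients, 7 in 86 and 8 in 95. One removed failure can decide the result when the count is at the boundary.

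**Working it through.** **1. Is there any route back into a safety analysis?** Take a treated patient whose breach is found later, and read the FAS sentence literally.

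- FAS: out, because the criteria were not met.
- FAS_RI: the same condition, so a roll-in patient in this position is out too.
- PPS: a subset of the FAS, so out.
- Safety analysis set: FAS, or FAS plus 18 from FAS_RI, so out.
- Safety sensitivity analysis 1 (protocol 14.2.10.2.1): "The primary safety endpoint analysis will be repeated with the FAS patients only if FAS_RI patients are added to the safety analysis set". Out.
- Safety sensitivity analysis 2: a tipping-point analysis for missing data within the safety analysis set. Out.
- Safety sensitivity analysis 3: the safety analysis set combined with FAS_RI. It is worded as an efficacy analysis, but even read as safety the patient is out.
- Protocol deviations (protocol 14.2.13, SAP 7.10): the breach is counted, but no outcome is analysed.

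No set of all patients in whom the device was used is defined.

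**2. Reproducing the plan's figures.** Inputs: performance goal 0.852, assumed rate 0.94, one-sided 5% level, Clopper-Pearson lower limit (protocol 14.1.2 and 14.2.10.2). For x event-free out of n, the lower limit L(x, n) is the 5th percentile of Beta(x, n − x + 1). Let c(n) be the smallest x with L(x, n) > 0.852. Type I error is P(X ≥ c(n)) at 0.852, and power is the same probability at 0.94.

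- Goal: the upper bound for 3/50 is the 95th percentile of Beta(4, 47) = 14.8%, which gives 85.2%. Matches.
- n = 78: c = 72, power 81.3%. n = 86: c = 79, power 85.6%. n = 95: c = 87, power 88.3%. All match.

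No stated sample size or power figure is wrong on this point.

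**3. Removing one failure.** The number and type of removals are assumptions; the documents give neither. If one failure is removed from N treated patients, x is unchanged and n becomes N − 1, so the test passes when x ≥ c(N − 1). Type I error becomes P(X ≥ c(N − 1)) with X binomial (N, 0.852).

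| N treated | c(N) | c(N − 1) | Type I, none removed | Type I, one failure removed |
|---|---|---|---|---|
| 86 | 79 | 79 | 4.9% | 4.9% |
| 95 | 87 | 87 | 4.7% | 4.7% |
| 100 | 92 | 91 | 3.1% | 6.1% |

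At 86 and 95 the required count does not drop, so nothing changes. At 100 it drops from 92 to 91, which adds P(X = 91) = 3.0%: 3.1% + 3.0% = 6.1%. In terms of the limit, L(91, 100) = 84.8% misses the goal and L(91, 99) = 85.9% meets it.

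**4. Other removals.**

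- One patient removed from 100 regardless of outcome: n = 99, type I error 3.4%, and power 86.0% against 85.4% at n = 100.
- 2% of all patients removed from 100 regardless of outcome: type I error 3.7%.
- 10% of failures and 2% of event-free patients removed from 100: type I error 6.7%.
- Two failures removed: 9.4% at 86, 8.9% at 95, 10.9% at 100.
- One event-free patient removed: type I error falls to 2.2% at both 86 and 95, and power falls from 85.6% to 74.2% and from 88.3% to 78.9%. Both are unchanged at 100.

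**The case against.** The best defence is that the plan already means eligibility as judged before device use. Protocol 7.2 makes enrolment a pre-device decision, and a subject who fails the check does not receive the device. The disposition section ties its exclusion to screening failures, which under 7.2 are untreated. The FAS sentence follows from an intention-to-treat premise. This makes the reading plausible. It does not settle the matter, because the FAS sentence adds meeting the criteria as a condition beside enrolment and no text fixes when that is judged. Exclusion 7 cannot be fully assessed before the device is used, since it reaches to drug use after the procedure.

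A reader might infer that the disposition section itself removes treated patients from every analysis. It does not support that, given the link between screening failure and non-use of the device. The problem lies in the FAS sentence.

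A reader might also infer that harm could be hidden. Adverse events are reported from enrolment, the CEC and DSMB review them, and deviations are tabulated, so such a patient would probably be visible. None of that changes the primary test.

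Finally, the figures above 5% assume removals that fall wholly or mainly on failures, and no passage links late-found breaches to outcome. That objection stands, and it limits the size of the claim.

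**Conclusion.** The point holds as a defect of wording in the set that decides the primary safety result. On its literal reading the FAS excludes a treated patient for a reason found after treatment, against the paragraph's own aim, and nothing else in the plan restores that patient.

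It would be too strong to say that the plan inflates type I error or that the safety result is biased. The documents do not say how many such patients exist, or whether removals would favour the device; with none, the effect is nil. Outcome-neutral removal keeps type I error below 5%, and one removed failure changes nothing at 86 or 95 patients. The doubling from 3.1% to 6.1% belongs to 100 patients and to a removed patient who is always a failure. The protocol plans approximately 100, and SAP 3 refers to enrolment having been discontinued, so the number actually analysed may differ.

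The FAS count also decides whether 18 roll-ins are added, so one removal at 79 patients would change who is tested. That jump comes mainly from the roll-in rule and adds no weight here.

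The change should be made because it is cheap and the result can turn on one patient. Confidence is medium, because the benign reading is plausible.

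**What to change.** In protocol 14.2.2.1 and SAP 7.2.1, and so for FAS_RI, state that:

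- FAS membership rests on eligibility as determined before device use.
- Every subject in whom the device was inserted or insertion was attempted stays in the FAS for primary safety and adverse event summaries, whatever is found later. This is in addition to enrolled, eligible subjects with no device attempt, whom the present FAS keeps and who should not be lost.
- Breaches found later are reported as protocol deviations. An analysis restricted to eligible patients is optional and is a sensitivity analysis only.

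In protocol 14.2.8 and SAP 7.5, state that the screening-failure exclusion covers only subjects in whom the device was not used.

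The timing in exclusion 7 and the pre-device check in protocol 7.2 must be reconciled.

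The cost is wording in two documents, with no new visits or data. The downside for the sponsor is that the reported safety rate may be slightly less favourable.

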14.2.2.2 Per-Protocol Analysis Set

The protocol definition of the TTH endpoint includes only those patients that received the test device and did not have adjunctive therapy other than light compression applied to the access site manually, with a dressing, or as per the investigator's standard procedure for suture-mediated closure devices. Therefore, the per-protocol analysis set (PPS) includes those patients in the FAS where the patient received the test device and did not have adjunctive therapy other than light compression.

14.2.2.3 Full Roll-In Analysis Set

The full roll-in analysis set (FAS_RI) are those patients that meet the same criteria as the FAS but are identified as roll-in patients.

14.2.2.4 Per-Protocol Roll-In Analysis Set

The per-protocol roll-in analysis(PPS_RI) set are those patients that meet the same criteria as the PPS but are identified as roll-in patients.

14.2.2.5 Efficacy Analysis Set

Due to the challenges during the pandemic, the number of patients in a non-missing primary efficacy endpoint may drop below the lowest accepted power (80%) for approval trial design (< 86 patients). If the number of patients in the PPS is ≤ 86 , the efficacy analysis set will include the patients in the PPS and the last 18 sequentially enrolled patients from the PPS_RI. If the number of patients in the PPS is > 86 , then the efficacy analysis set will only include PPS patients.

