14.1.1 Primary Efficacy Endpoint

The primary effectiveness hypothesis will be tested by comparing the primary effectiveness endpoint, mean time-to-hemostasis (TTH), against a performance goal (PG) of 15 minutes.

The comparison to the performance goal will be based on the following statistical hypothesis test:

$$H_0: \mu_{TTH} \geq 15$$

$$H_A: \mu_{TTH} < 15$$

where μ_{TTH} is the mean time-to-hemostasis in minutes.

The test will be based on whether the upper one-sided 97.5% confidence limit (based on a t-distribution)^{iv} is less than 15. Assuming similar performance to Perclose ProGlide®, with a mean time-to-hemostasis of 9.8 minutes and a standard deviation of 17 minutes the sample sizes for power levels from 80 to 90%

a Table 3: Primary Efficacy Endpoint Sample Sizes for Various levels of Power

Power	Sample Size	Maximum Observed Time (minutes) and still reject H_0
80.0%	86	10.8
81.4%	89	10.9
82.3%	91	10.9
83.1%	93	10.9
84.3%	96	11.0
85.0%	98	11.1

Successful rejection of the null hypothesis will mean that the PG has been met.

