14.2.3 Poolability Analyses

All investigational sites will follow the requirements of a common protocol and standardized data collection procedures and forms. The primary endpoints will be presented separately (major and minor complications will be presented separately for the primary safety endpoint) for each site using descriptive statistics. Poolability of the primary endpoints across the investigational site will be evaluated using a regression model with fixed effects for the site using the FAS for the primary safety endpoint and PPS for primary efficacy endpoint. Sites enrolling less than five subjects will be combined with the geographically nearest site. If the p-value for the site effect is <0.15 , additional exploratory analyses will be performed to understand any variations in outcomes by site.

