##### Summary Statements

Statistical Analysis Plan		Page 26 of 31
Sponsor Terumo Medical Corporation	Study Cross-Seal IDE Trial: Prospective, Multi-Center, Single Arm Study of the Cross-Seal Suture-Mediated Vascular Closure Device System	Version 1.4

A sample size of 86 achieves 80% power to detect non-inferiority using a one-sided one-sample t-test when the non-inferiority mean is 15.0 and the actual mean is 9.8. The data are drawn from a single population with an estimated standard deviation of 17.0. The significance level (alpha) of the test is 0.025.

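### The roll-in top-up counts set members at 86 or fewer (78 or fewer for safety), although its stated reason is fewer than 86 (78) non-missing endpoints, and no analysis compares roll-in with pivotal subjects

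*Protocol*

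**What the plan says.** Protocol 14.2.2.5 (SAP 7.2.5) gives the reason for the efficacy top-up: the number of patients with a non-missing primary efficacy endpoint may "drop below the lowest accepted power (80%) for approval trial design (< 86 patients"). The operative sentence counts something else. If the PPS has 86 members or fewer, "the efficacy analysis set will include the patients in the PPS and the last 18 sequentially enrolled patients from the PPS_RI". Above 86, only the PPS is used.

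Protocol 14.2.2.6 (SAP 7.2.6) has the same structure for safety. The reason is fewer than 78 non-missing endpoints; the trigger is an FAS of 78 or fewer; the addition is "the last 18 sequentially enrolled patients from the FAS_RI".

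The efficacy floor comes from the SAP appendix: "A sample size of 86 achieves 80% power to detect non-inferiority using a one-sided one-sample t-test". The safety floor of 78 carries 81.3% power in Protocol 14.1.2.

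Roll-ins are each investigator's first one or two cases, set apart for gaining experience with the device (Protocol 2.2).

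The site poolability model in Protocol 14.2.3 (SAP 7.3) is run "using the FAS for the primary safety endpoint and PPS for primary efficacy endpoint". The subgroup models in 14.2.11 use the efficacy and safety analysis sets instead.

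Protocol 14.2.10.1.1 and 14.2.10.2.1 plan repeats of the primary analysis without the added roll-ins and with all of them. The third safety item names the efficacy endpoint, apparently a slip.

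**The concern.** The reason and the rule differ in two ways: evaluable patients against set members, and strictly below against at or below. The rule can therefore act when its reason is absent and stay silent when its reason is present. Its size is also unrelated to the shortfall, so it need not deliver the power by which it is justified.

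The topped-up sets decide study success (14.2.10). When the rule fires, learning-phase cases form about a fifth of the primary efficacy set, and the plan has no direct check that they behave like the pivotal cases.

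**Working it through.** **Inputs**
- Efficacy: tested "against a performance goal (PG) of 15 minutes", "with a mean time-to-hemostasis of 9.8 minutes and a standard deviation of 17 minutes", one-sided alpha 0.025 (Protocol 14.1.1, SAP 9.1).
- Safety: null 85.2%, assumed 94%, one-sided alpha 0.05, exact test (Protocol 14.1.2, SAP 9.2).
- Top-up: 18 if PPS ≤ 86, or if FAS ≤ 78.

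**Step 1: reproduce the plan's figures.** Efficacy power is 1 − F(t₀.₉₇₅,N−1), where F is the noncentral t distribution with N−1 degrees of freedom and noncentrality (15 − 9.8)/17 × √N.
- At N = 86 the noncentrality is 0.3059 × 9.274 = 2.837 and the critical value 1.988, giving power 0.8008, as in SAP 9.1. The other five rows also reproduce.
- N = 85 gives 79.6%, so 86 is the smallest N reaching 80%.
- For safety, the critical count r is the smallest with P(X ≥ r | N, 0.852) ≤ 0.05, and power is P(X ≥ r | N, 0.94). At N = 78, r = 72 and power is 81.3%; at N = 86, r = 79 and 85.6%; at N = 95, r = 87 and 88.3%. All three match.

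**Step 2: apply the efficacy rule as written**, with every member evaluable and 18 roll-ins available.

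| PPS | Short of 86 by | Added | N | Power | Roll-in share |
|---|---|---|---|---|---|
| 60 | 26 | 18 | 78 | 76.0% | 23.1% |
| 67 | 19 | 18 | 85 | 79.6% | 21.2% |
| 68 | 18 | 18 | 86 | 80.1% | 20.9% |
| 80 | 6 | 18 | 98 | 85.0% | 18.4% |
| 85 | 1 | 18 | 103 | 86.8% | 17.5% |
| 86 | 0 | 18 | 104 | 87.1% | 17.3% |
| 87 | 0 | 0 | 87 | 80.5% | 0% |

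From PPS 86 to 87 the analysed N falls by 104 − 87 = 17. The floor is restored only for PPS of 68 or more.

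**Step 3: the safety rule.**

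| FAS | N used | r | Power |
|---|---|---|---|
| 59 | 77 | 72 | 68.4% |
| 60 | 78 | 72 | 81.3% |
| 62 | 80 | 74 | 79.6% |
| 67 | 85 | 79 | 75.2% |
| 76 | 94 | 87 | 79.7% |
| 78 | 96 | 88 | 87.8% |
| 79 | 79 | 73 | 80.5% |

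The stated N of 78 is restored for FAS of 60 or more (60 + 18 = 78). Exact power is not monotone in N: totals of 80 to 85 give 79.6% down to 75.2%, and 94 gives 79.7%. Reaching 78 or more is therefore not the same as having 80% power.

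**Step 4: the counting mismatch.** A PPS of 87 with two TTH values missing leaves 85 evaluable (79.6%) and no top-up. An FAS of 79 with two 30-day statuses missing leaves 77 (68.4%) and no top-up. The plan itself provides for missing values: 14.2.6 has tipping-point analyses for subjects without a TTH and without a 30-day visit, and the SAP appendix allows 10% dropout.

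**Step 5: poolability.** The 14.2.3 model has a site term only and is fitted to the FAS and PPS. Added roll-ins are in the 14.2.11 regressions, but those have terms for gender, age group and race only. No planned model contrasts roll-in with pivotal subjects.

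**The case against.** **The inequality alone matters at one integer per endpoint**, and the fixed 18 was prespecified in a SAP version issued after regulatory feedback (SAP 1). Both statements stand. A reader might infer that a fixed 18 is an error and that roll-ins must be added one at a time until the floor is reached. The documents do not support that. It is a debatable alternative, and for safety a fragile one: stopping at exactly 78 leaves one missing status between 81.3% and 68.4%.

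**Some surplus over the floor fits the plan.** The appendix inflates 86 to 96 and 78 to 87 for dropout. That stands, but it argues for counting evaluable patients, which the trigger does not do.

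**The planned repeats show the result without roll-ins.** This is a real safeguard. A reader might infer that the topped-up result stands alone, or that no model includes the added cases; neither is so. What is missing is narrower: a site model on the topped-up sets and a roll-in versus pivotal contrast.

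**The low end may never occur.** A PPS of 67 would be about a third below the roughly 100 planned pivotal subjects, and the documents give no count. TTH is measured during the index procedure, so missed follow-up visits do not remove it. The pilot TTH values all lay within 0 to 13 minutes, so the efficacy floor may not bind in practice. These points limit the size of the efficacy concern. They do less for safety, where missed follow-up is the stated problem.

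**The 68.4% figure is a trough.** Much of that loss is binomial discreteness, and it should not be read as typical of a large shortfall.

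**Conclusion.** The concern holds as a mismatch between rule and reason. The trigger should count non-missing endpoints and be strict. As written, it adds 18 roll-ins at exactly 86 or 78 evaluable patients, where power is already 80.1% or 81.3%, and can miss a real shortfall just above the threshold. The top-up restores the stated N only for PPS ≥ 68 or FAS ≥ 60, and for safety that N does not guarantee 80% at every larger total. Roll-ins make up 17% to 21% of the efficacy set for PPS 68 to 86 without a direct comparison with pivotal subjects.

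A reader might go further and infer bias or an inflated type I error from the roll-ins. The documents contain no data showing that roll-in outcomes differ, in either direction.

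The figures assume that the FAS and PPS hold pivotal subjects only (the rule makes sense only then, though 14.2.2.1 does not say so), that 18 roll-ins are available and evaluable, and that roll-ins share the pivotal mean, SD and event rate. The last has no basis in the documents.

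**What to change.** (a) In Protocol 14.2.2.5–14.2.2.6 and SAP 7.2.5–7.2.6, trigger the top-up when patients with a non-missing primary endpoint number fewer than 86 (efficacy) or fewer than 78 (safety, with missing as defined in 14.2.5). State that the FAS and PPS counts exclude roll-ins.

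(b) Keep the prespecified 18 if preferred, but report the exact power at the evaluable N achieved, and do not claim that the top-up restores 80% at every shortfall.

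(c) In Protocol 14.2.3 and SAP 7.3, run poolability on the efficacy and safety analysis sets actually used, with a roll-in versus pivotal term whenever roll-ins are included.

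**Cost.** This is SAP wording and one model term. At exactly 86 or 78 evaluable patients N is 18 smaller. With 18 retained, the jump in N moves rather than disappears: 103 at 85 evaluable, 86 at 86. The new term will be imprecise. For 18 roll-ins against 80 pivotal subjects at SD 17, the standard error of the difference is 17 × √(1/18 + 1/80) = 4.4 minutes, a 95% half-width of about 8.8 minutes against the assumed gap of 15 − 9.8 = 5.2. It should be reported as an estimate with its interval, not used as a pass or fail test for pooling.
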